## Psychophysical Testing A: Photostress / Glare / Chromatic Contrast

#### Apparatus

Four efficacy parameters will be measured (heterochromatic contrast threshold (HCT), photostress recovery [PR] time, glare disability [GDs], and glare discomfort [GDc]). All tests will utilize the same apparatus, modified for each parameter. The apparatus used to measure HCT, GDs, GDc, and PR is a two-channel Maxwellian view system and is shown in Figure 2 and Figure 3.

The glare source (annulus/disk) and the visual target will be produced by a 1000 Watt xenon arc point source lamp, with a modified housing that allows dual-channel exit (Newport Optics; Irvine, CA). Alignment of the subject's eye with the optical system will be maintained with a forehead rest and a dental impression bite bar that will be custom-fit for each subject. An auxiliary optical channel with a high-resolution camera and monitor will be used to monitor the pupil during testing to ensure proper fixation and sustained alignment, and will be used to measure GDc. The same apparatus, with small variations, will be used to test HCT, GDs, and PR.

All photometric calibrations will be performed using a PR-650 SpectraScan Colorimeter (Photo Research, Inc., Chatsworth, CA). Wedge and neutral density radiometric calibrations will be performed by using a Graseby Optronics United Detection Technology (UDT) instrument (Orlando, FL). The same UDT instrument will be used before every experimental session to ensure that the total light output of the optical system remains constant and consistent throughout the study. The PR-650 can make measurements down to about 380 nm. An additional radiometer (General Tools and Instruments; New York, NY) will be used to measure output farther down into the UV portion of the spectrum.

#### **Investigational contact lenses**

The Investigational lenses will be tested without an additional UV/HEV light source.

#### The test target

The visual target will be the same in all the visual function tests (HCT, GDc, GDs, PR).

#### The background

The background channel will be manipulated to produce either an annulus (for GDs) or a three-degree background field (for GDc and PR). For the HCT test, the same three-degree background will be filtered through a 460 nm interference filter (half-power bandwidth = 8 nm; Edmund Optics; Barrington, NJ) in order to produce a monochromatic field. Xenon was selected as the light source because it has the characteristic broad band emission spectrum (as assessed by the SpectraScan colorimeter) with a CIE chromaticity of u' = 0.25, v' = 0.53. Xenon is widely regarded as a good match for sunlight. For example, in a study of 26 solar simulators, the authors noted that xenon-arc light sources match the most accurately. The xenon spectrum that will be produced by this system is shown in Figure 4 as compared to mid-day sunlight.

JJVC CONFIDENTIAL

[figure not shown]

Figure 4: The xenon (dark line) compared to noon day sun light (red line). The line in red is taken from the NASA solar spectrum measured at the earth's surface  and adjusted along the ordinate with respect to the xenon source that will be used in this study.

JJVC CONFIDENTIAL

	Psychophysical Testing A: Photostress / Glare / Chromatic Contrast		
Т	The psychophysical tests described in Steps 1-4 below may occur in any order. No additional UV/HEV activation light source will be used.		
Step	Procedure	Details	
1	Glare Disability (GDs)	The target stimulus will be presented for 2 seconds on and 1 second off to reduce the chances that subjects will habituate to the stimulus. A second channel will provide an annulus with an approximately 11-degree inner diameter and 12-degree outer diameter, as shown below.	
		Before each trial, the annulus will be set at a level well below that which would cause the target stimulus to be veiled. The experimenter will then adjust, via the neutral-density wedge, the intensity of the annulus until the target stimulus is no longer visible. Participants will indicate that the target has been veiled by pressing a buzzer.	
		The experimenter increases the intensity of light scattering within the subjects' test eyes until they cannot effectively see. Unlike the photostress bleach which is set and standard, the intensity is varied in this test, and hence, so is the aversiveness of the dependent variable. This measurement has been conducted successfully, repeatedly, in the past 	
2	Heterochromatic Contrast Threshold (HCT)	Chromatic contrast will be measured as thresholds to a variable wavelength central target presented on a short-wave (460 nm) sky-light background. This aspect of the testing is mostly exploratory to see how the contacts influence chromatic contrast. The relation to filtering is very strong as long as there is differential filtering between the target and the background.	
		Stimulus size Stimulus size	

Page 39 of 117

	Psychophysical Testing A: Photostress / Glare / Chromatic Contrast			
3	Photostress Recovery (PR)	To measure PR time, participants are exposed to the same target used in each of the other visual function tests. Once the participant is comfortably viewing the target, the experimenter will cover the target with a bright, bleaching light. Exposure to the light will cause participants to momentarily lose sight of the target, which will be covered by an afterimage. As the afterimage fades, participants will gradually be able to re-gain sight of the target. PR time will be recorded as the time it takes following exposure to the bleaching light to regain sight of the target.		
4	Glare Discomfort (GDc)	
 
Glare discomfort (GDc) will be quantified using the squint response and a questionnaire. The discomfort that accompanies exposure to light in excess of an individual's adaptive state is accompanied by contraction of the extraocular muscles (squint). The squint response has been shown to be a valid objective indicator of glare discomfort. This procedure was described by Gowrisankaran. Degree of squint is calculated as the ratio of the height of the palpebral fissure under normal lighting conditions compared to maximal squint produced during the photostress exposure. A high-resolution camera (AmScope MU300 digital camera; Irvine, CA) will be used and calibrated against a spatial standard before the start of each day of testing. The resultant videos will be analyzed as still frames using AmScope measurement software (Irvine, CA). To determine subjective ratings of GDc, subjects will be asked to rate the degree of discomfort of the photostressor using a single-item questionnaire OD and OS:
 
How bothersome was the glare that you just experienced? Subjects will have the following response options: Extremely bothersome, Very bothersome, Somewhat bothersome, A little bothersome, Not at all bothersome.
 
		

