## 4.2. Study Design Rationale

This study will be executed using a contralateral design. There are several benefits to this choice of design. First, we intend to relate performance with the investigational lens in its activated and inactivated states to baseline light sensitivity. A contralateral design will allow us to compare performance with both activation states within the same individual, ostensibly with the same baseline light sensitivity. Second, other subject factors that can influence visual performance, such as iris color and absorption of test lights via macular pigment, are better controlled using this design. Third, in psychophysical testing, which is the gold standard for many of the visual functions being tested, participants make judgments about some event threshold, such as when an image disappears or how large or bothersome or intense a visual event appears. Participants may have different criteria for threshold events that are internally consistent *within* subjects but can vary *between* subjects. A contralateral design allows the investigational lens to be compared within subjects, with consistent criteria for threshold events. Given the fact that sufficient time will be taken between measures, in some cases 24 hours or more, carryover effects are unlikely.

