		Calipers are adjusted until the inner edges are just touching the edges of the starburst pattern. minutes. Record values OD and OS, in mm (2 decimal places). Subjects will respond to a single-item post- starburst questionnaire OD and OS: • How severe / intense was the starburst that you experienced? Subjects will have the following response options: Severe, moderate, mild, not at all.		

	Psychometric Testing B: Dysphotopsia Evaluation				
	The psychophysical tests described in Steps 1-3 below may occur in any order. All three tests will perfomed twice: once with an UV/HEV activating light source and once with no activating light source. The order of light source testing will be randomized.				
Step	Procedure	Details			
3	Halos	Subjects will have the nature of halos explained using visual aids prior to the experiment. The halo measurement will utilize the same light source as the starburst and two- point measures to produce the halo. The same calibrated micrometer from the starburst test will be used to define the outer edges of the halo image (investigator adjusting based on subject feedback). Ascending and descending methods of limits will be used. This measurement takes about 10-15 minutes. Record values OD and OS, in mm (2 decimal places). Subjects will respond to a single-item post-halo questionnaire OD and OS:			
		• How severe / intense was the halo that you experienced? Subjects will have the following response options: Severe, moderate, mild, not at all.			
4	Repeat	The steps above will be repeated but with the alternate light source testing method. The investigator must allow at least 10 minutes to lapse before starting the second round of testing.			

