## 14.6. Secondary Analysis

## Photostress Recovery Time (Seconds)

Photostress recovery time (PSRT) will be evaluated by exposing subjects to an intense light source (10-deg circular broad-band white at ~4.5 log Tds) and will be quantified as the time necessary to regain site of the grating after exposure.

PSRT will be analyzed using a linear mixed model. Sequence of lens wear, lens type, age group dominant eye and all the interaction between lens type and age group will be included as fixed

effects. An appropriate covariance structure will be used to model the residual errors between measurements between eyes within a subject. The variance-covariance structure will be selected based on the finite-sample corrected Akaike's Information Criterion Corrected (AICC). The structure that returns the lowest AICC will be deemed the most appropriate structure. Covariance structures under consideration include:

- Unstructured (UN)
- Compound Symmetry (CS)
- Heterogeneous Compound Symmetry (CSH)

Heterogeneous covariance structures across lens type may be considered if necessary. The Kenward and Roger method (Kenward and Roger, 1997) will be used for the denominator degrees of freedom.

Comparisons between lenses will be carried out using 2-sided 95% confidence intervals constructed for the least-square mean (LSM) difference (Test – Control). Statistically significantly lower differences of the Test lens relative to the Control lens will be concluded if the upper limit of the 95% confidence interval is below 0. If the interaction between lens type and age is significant then comparisons between lenses will be made within age group.

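### Testing A allows the photostress bleach to precede the glare-disability and contrast tests with no stated recovery time, so these two secondary endpoints could carry a residue that differs by lens

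*Combined protocol and SAP*

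**What the plan says.** Section 7.2 lists the Testing A tests as glare disability (GDs), heterochromatic contrast threshold (HCT), photostress recovery (PR) and glare discomfort (GDc). Above the list it states: "The psychophysical tests described in Steps 1-4 below may occur in any order". The visual target is the same in all four.

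In the PR step, "the experimenter will cover the target with a bright, bleaching light", and an afterimage then hides the target. The endpoint is defined by first return of visibility: "PR time will be recorded as the time it takes following exposure to the bleaching light to regain sight of the target". GDc belongs to the same event, because palpebral fissure height in normal light is "compared to maximal squint produced during the photostress exposure". Section 14.6 gives the bleach as "10-deg circular broad-band white at ~4.5 log Tds". Section 7.2 gives a three-degree field for PR and GDc; the two sizes need reconciling, but under either description the light covers the target.

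On spacing, Section 4.2 says: "Given the fact that sufficient time will be taken between measures, in some cases 24 hours or more, carryover effects are unlikely". Testing B is more specific: "The investigator must allow at least 10 minutes to lapse before starting the second round of testing". Testing A states no interval and no check that sensitivity has returned.

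The Section 14.6 model for PR, applied also to GDs and HCT, contains lens-wear sequence, lens type, age group, dominant eye and lens type by age group. It has no term for test order or time since the bleach, and no procedure step asks for the order to be recorded.

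**The concern.** GDs and HCT both depend on how well the subject sees the target that the bleach has just hidden. If either is measured after the bleach and before full recovery, the reading includes some leftover photostress.

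The residue matters most if it differs between the two eyes of a subject. Section 7.2 describes the bleach source as fixed ("Unlike the photostress bleach which is set and standard"), but what reaches the retina passes through the lens. Section 1.2 says the investigational lens is meant to attenuate bright light, and secondary hypothesis 1 in Section 2.3 predicts shorter recovery in the Test eye. If either holds, a Test–Control difference in GDs or HCT could partly re-measure photostress, although Section 2.3 treats the secondary hypotheses as independent. With order unrecorded, the analysis could not separate the two afterwards.

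**Working it through.** The plan states no figure on this point, so the check is of the text, followed by an illustration on assumed values.

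**1. Does any passage close the gap?**
- Order: left free in Section 7.2; neither fixed nor randomised.
- Interval: the 24 hours in Section 4.2 matches the minimum gap between visits in Sections 4.1 and 4.3. All four Testing A tests fall within Visit 1, so what remains for them is an assurance with no duration. The 10 minutes applies to the two rounds of Testing B.
- End of PR: the target is seen again. That is one visibility criterion, not a return to baseline.
- Analysis: no order term in Section 14.6.

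**2. Which endpoints are exposed?** PR is the bleach test itself and GDc is read during the bleach. That leaves GDs and HCT. The primary endpoints are measured at Visit 2, at least 24 hours later.

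**3. When is it bias and when is it noise?** For subject i, write the paired difference as

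D_i = δ + (c_iT − c_iC) + e_i,

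where δ is the lens effect and c_iT, c_iC are the residues in the Test and Control eyes. The bias is the mean of c_iT − c_iC. A residue common to both eyes cancels from the mean, though a varying order and wait still add scatter. A residue that depends on the lens does not cancel: it moves with the lens whichever eye wears it, so lens-to-eye randomisation does not balance it.

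**4. Illustration: effect of the wait.** Assume that a between-lens difference in bleach decays as exp(−w/τ), with w the wait and τ the same in both eyes. Both are assumptions. For example, τ = 120 s and w = 120 s gives exp(−1) = 37%.

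| Assumed τ | 60 s wait | 120 s | 300 s | 600 s |
|---|---|---|---|---|
| 60 s | 37% | 14% | 0.7% | 0% |
| 120 s | 61% | 37% | 8% | 0.7% |
| 240 s | 78% | 61% | 29% | 8% |
| 400 s | 86% | 74% | 47% | 22% |

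These are shares of an unknown starting difference. They show that the unstated wait decides whether carry-over is negligible; they do not size it.

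**5. Illustration: effect on a test.** Take 60 completers (Section 14.2), no true lens effect, and a bias of d standard deviations of the paired difference. A paired t-test stands in for the mixed model. The chance that the 2-sided 95% interval excludes zero on the side of the bias is P(T > t(0.975; 59)), with T noncentral t on 59 degrees of freedom and noncentrality d√60.
- d = 0: 2.5%
- d = 0.05: 5.7%
- d = 0.1: about 12%
- d = 0.2: 33%
- d = 0.3: 63%

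The documents give no standard deviation for GDs or HCT, so the values of d are assumptions.

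**The case against.** The strongest reply is that practice may already be safe. The listed order puts PR and GDc last, so a tester who follows the list finishes both visibility tests before any bleach in that eye. Section 4.2 promises adequate spacing, and its reference to some cases of 24 hours implies shorter gaps elsewhere, so it can be read as covering tests within a visit. Section 7.2 allows about two hours of lens wear, and the background channel has to be reconfigured between tests. Testing A also uses no added activating light, so the Test lens may attenuate the bleach only slightly.

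Much of this stands. The Section 4.2 sentence is vague rather than shown to be wrong, and nothing says that GDs or HCT starts as soon as the target reappears. But none of it binds the tester: the order rule expressly allows departures from the list, and no duration backs the assurance. The absence of an activating light does not settle the matter either, since secondary hypothesis 1 predicts faster recovery in exactly that state.

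Three stronger readings are tempting and are not supported.
- A reader might infer that the bleach precedes at least one of GDs and HCT in 2/3 of subjects and both in 1/3. That follows only if the three are in random order. The plan leaves order unspecified, and if testers follow the list the figures are zero.
- A reader might take the decay percentages as the size of the bias. They rest on assumed constants, and only a between-lens difference biases the comparison.
- A reader might infer that unmasked site staff (Section 5.2) could use the free order to favour a lens. Nothing says that order differs between a subject's two eyes, and a shared order offers no obvious way to do so.

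**Conclusion.** The gap is real but limited. The plan permits a bleaching exposure before GDs and HCT on the same target, states no recovery time, and neither records nor models order. Bias requires two further conditions: that some subjects are tested in that order with too short a wait, and that the residue differs by lens. The documents show neither, but their own expectations make the second plausible.

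The size cannot be derived. Nor may one infer that carry-over would favour the Test lens on both endpoints. For GDs, a less bleached Test eye would be expected to hold the target in view against a stronger annulus, which is the direction of secondary hypothesis 2. For HCT the direction is open. Hypothesis 4 predicts a higher Test threshold; if threshold means the light needed to see the target, as Section 7.2 suggests, a less bleached eye would have a lower one. Section 14.6 describes the quantity differently again.

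Only two secondary endpoints are exposed, and Section 7.2 calls HCT mostly exploratory. The primary endpoints are unaffected. The change is worth making because it is nearly free beforehand and cannot be recovered in analysis afterwards.

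**What to change.** In Section 7.2, Testing A, replace the free-order rule with one fixed order for every subject: complete HCT and GDs in both eyes before any photostress exposure, then take PR and GDc. This makes binding what the listed order already suggests, and it needs no assumed recovery time. Align the carry-over sentence in Section 4.2, so that within Visit 1 it rests on this order rather than on unspecified spacing.

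The change adds no test, visit or staff. Finishing both eyes before the first bleach may mean re-aligning each eye on the bite bar. A fixed order can also carry a fatigue or practice effect, but one common to both lenses. A stated interval or recovery check before GDs and HCT, with order recorded and modelled, would be an alternative, but it needs a recovery time that the documents do not supply.

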#### Psychometric Testing B: Dysphotopsia Evaluation

#### Apparatus

Three efficacy parameters will be measured (two-point light spread functions, halos, starbursts) for three lens conditions (OASYS, investigational lens without additional UV/HEV light source, investigational lens with additional UV/HEV light source). All tests will utilize the same apparatus, modified for each parameter.

The general optical apparatus is shown in Figure 6 and Figure 7.

The light source will be produced by a 250 Watt xenon arc point source lamp. Alignment of the subject's eye with the optical system will be maintained with a forehead and chin rest assembly. All photometric calibrations will be performed using an ILT 950 (Peabody, MA). and a Graseby Optronics United Detection Technology (UDT) instrument (Orlando, FL). The same UDT instrument will be used before every experimental session to ensure that the total light output of the optical system remains constant and consistent throughout the study. The PR-650 can make measurements down to about 380 nm. An additional radiometer (General Tools and Instruments; New York, NY) will be used to measure output farther down into the UV portion of the spectrum.

#### Investigational contact lenses

The investigational lenses will be tested with an additional UV/HEV light source as one of the test conditions. "Activation" will be achieved using an ultraviolet activator consisting of LEDs waveband 365-400 nm that combines with the primary optical path of the system, after the final lens of the optical system (see Figure 7). The spectral output of the ultraviolet LEDs is given in Appendix G. The ultra-violet LEDs will be used, at a low constant rate, while the visual measures (halos, etc.) are being collected. The overall energy at the plane of the eye is 64  $\mu$ w/cm2 (measured using the ILT 950, the graph in Appendix G is the light source at the energy we plan to use during the measurement). As a comparison, the UV activator emits 0.07 mw/cm2 whereas mid-day sunlight measured 11 mw/cm2 using the same instrument (1:00 PM, partially cloudy day, September 18, 2017, Athens, GA using a UVA light meter: General UV254SD).

JJVC CONFIDENTIAL

JJVC CONFIDENTIAL

	Psychometric Testing B: Dysphotopsia Evaluation			
	The psychophysical tests described in Steps 1-3 below may occur in any order. All three tests will perfomed twice: once with an UV/HEV activating light source and once with no activating light source. The order of light source testing will be randomized.			
Step	Procedure	Details		
1	Two-point Light Spread Function	These thresholds are defined as the minimum distance that two points of light are completely distinct. An ascending and a descending method of limits will be used. This measurement takes about 10-15 minutes. Record values OD and OS, in mm (2 decimal places).		
2	Starburst	This is defined as the diameter of the light's lateral spread. Subjects will have the nature of starbursts explained using visual aids prior to the experiment. The investigator will adjust a calibrated custom-made micrometer (two sides with reverse threading) to spread two posts out from a central mid-point. Those posts will be used to define the outer boundaries of the starburst image. Ascending and descending methods of limits would be used based on subject feedback. This measurement takes about 10-15		
		Calipers are adjusted until the inner edges are just touching the edges of the starburst pattern. minutes. Record values OD and OS, in mm (2 decimal places). Subjects will respond to a single-item post- starburst questionnaire OD and OS: • How severe / intense was the starburst that you experienced? Subjects will have the following response options: Severe, moderate, mild, not at all.		

	Psychometric Testing B: Dysphotopsia Evaluation				
	The psychophysical tests described in Steps 1-3 below may occur in any order. All three tests will perfomed twice: once with an UV/HEV activating light source and once with no activating light source. The order of light source testing will be randomized.				
Step	Procedure	Details			
3	Halos	Subjects will have the nature of halos explained using visual aids prior to the experiment. The halo measurement will utilize the same light source as the starburst and two- point measures to produce the halo. The same calibrated micrometer from the starburst test will be used to define the outer edges of the halo image (investigator adjusting based on subject feedback). Ascending and descending methods of limits will be used. This measurement takes about 10-15 minutes. Record values OD and OS, in mm (2 decimal places). Subjects will respond to a single-item post-halo questionnaire OD and OS:			
		• How severe / intense was the halo that you experienced? Subjects will have the following response options: Severe, moderate, mild, not at all.			
4	Repeat	The steps above will be repeated but with the alternate light source testing method. The investigator must allow at least 10 minutes to lapse before starting the second round of testing.			
5	On-eye Light Transmission	Measuring the in vivo light transmission (alternatively, the optical density) of ophthalmic lenses has been described in detail elsewhere using similar optical systems. The optical density (OD) of the test lens will be derived by comparing these threshold values to the rhodopsin curve, adjusted to a maximum OD equal to 0.35. This procedure obviously measures the density of all the ocular media. However, because the majority of the absorbance is due to the lens, the convention of referring to these values simply as lens density will be used. Given the extra time needed to perform this measurement, and the fact that on eye light transmission will be constant across all subjects (this reflects properties of the optical system and lenses, themselves, as opposed to visual performance of individuals wearing the lenses), these measurements will be taken in a small subset of subjects (n=5) who, when scheduled, report having enough extra time to complete the measurements.			

# VISIT 2

Subjects must enter Visit 2 wearing their own contact lenses.

Visit 2: Treatment 2			
Step	Procedure	Details	
2.1.	Adverse Events and Concomitant Medications Review	Review any changes to the subject's medical history or concomitant medications from the previous study visit. Record any changes, and any adverse events.	
2.2.	Entrance Visual Acuity	Record the distance Snellen visual acuity (OD, OS, and OU) to the nearest letter with their habitual correction in place. Subjects must read the smallest line until at least 50% of the letters are read incorrectly.	
2.3.	Remove Habitual Lens	If applicable, the subject's habitual contact lenses will be removed and stored in their own lens case. If they forgot to bring their lens case, one will be provided to them.	
2.4.	Slit Lamp Biomicroscopy	FDA Slit Lamp Classification Scale will be used to grade the findings and determine eligibility. If any of these slit lamp findings are grade 3 or higher, the subject may not continue at this time, but may return up to one additional time to determine eligibility. If discontinued a final examination must be completed. If the clearance of the fluorescein needs to be expedited, preservative-free rewetting drops or saline may be instilled.	
2.5.	Continuance after Baseline	All responses to Inclusion Criteria questions must be answered "yes" and all responses to Exclusion Criteria questions must be answered "no" for the subject to be considered eligible. This refers to the concomitant medications and slit lamp biomicroscopy. If subject is deemed to be ineligible after two baseline attempts at Visit 2, proceed to Final Evaluation and complete all forms.	
2.6.	Lens Selection	Assign the study lens based on the randomization scheme.	

	Visit 2: Treatment 2			
Step	Procedure	Details		
		Select the contact lens power based on the refraction from Visit 1 or the final lens power from Visit 1. Record the test condition.		
2.7.	Lens Insertion	The Investigator or the subject inserts the study lenses. Record the time of lens insertion. Check for lens damage under the slit lamp before proceeding with lens settling. Replace damaged lenses if applicable.		
2.8.	Lens Settling 1	Allow the study lenses to settle at least 5 minutes before continuing.		
2.9.	Subjective Best Sphere Over Refraction	Perform subjective best sphere refraction over the study lenses (adopt the maximum plus to maximum visual acuity (MPMVA) approach.		
2.10.	Lens Power Modification (if applicable)	Adjust the lens power if the subject's best sphere over-refraction is not plano. For any power modification, repeat steps 2.7- 2.9). One power modification is allowed.		
2.11.	Lens Settling 2	Please wait for at least 10 minutes from final lens insertion to continue.		
2.12.	Subject Reported Ocular Symptoms	Subjects will respond to a verbal open-ended symptoms questionnaire.		
2.13.	Visual acuity	Record the best corrected Snellen distance visual acuity to the nearest letter (OD and OS). Subjects must read the smallest line until at least 50% of the letters are read incorrectly.		
2.14.	Subjective Lens Fit Assessment	
 
Evaluate overall lens fit acceptance (acceptable or unacceptable) based on centration, movement and other fitting characteristics.
 
An unacceptable fit is deemed by one of the following criteria: 
 
limbal exposure at primary gaze or with extreme eye movement
 
edge lift
 
 
 
		

	Visit 2: Treatment 2			
Step	Procedure	Details		
		
 
excessive movement in primary and up gaze
 
insufficient movement in all three of the following conditions: primary gaze, up gaze, and Josephson push up
 
Note: if lens fit is unacceptable subject will be discontinued from the study.
 
		
2.15.	Continuance	
 
For the subject to continue in the study, they must meet all three of the following criteria: 
 
Visual acuity is 20/30 or better OD and OS
 
The lens fit is acceptable OD and OS
 
Investigator approval.
 
 
 
If the Investigator does not approve the wearing of the study lenses for the psychophysical testing, then the study is terminated for that subject.
 
		
2.16.	Lenses Worn in Clinic	
 
The lenses will be released for approximately two hours.
 
1. The subjects must wear both study lenses the entire time.
 
2. The lenses will be worn as daily wear only.
 
3. Rewetting drops are permitted if needed.
 
Note: In the event a lens is lost or damaged, it will be replaced immediately.
 
Note: A clinic-only-wear Patient Instruction Guide will be provided.
 
		
2.17.	Sequence Randomization	At Visit 2, all subjects will proceed to Psychophysical Testing B: This includes 2- point light threshold, haloes, and starbursts. Five subjects that are willing to undergo further in vivo light transmission testing will have this procedure performed. Following the psychometric testing by the co- investigator, the subject will return to the principal investigator to complete the study visit as described in steps 2.18 – 2.19.		

	Visit 2: Treatment 2			
Step	Procedure	Details		
2.18.	Lens Removal	The worn study lenses will be removed and discarded.		
2.19.	Exit Slit Lamp Biomicroscopy	FDA Slit Lamp Classification Scale will be used to grade the findings and determine eligibility.		
		Ocular adverse events shall be those that grade 3 or 4 on the FDA scale. The study monitored must be notified immediately. The AE will be followed to resolution.		
		If the clearance of the fluorescein needs to be expedited, preservative-free rewetting drops or saline may be instilled.		

